5.3 Inclusion and Exclusion Criteria

Inclusion and exclusion criteria deviations will be presented in a data listing.

5.4 Treatment Compliance

All doses of the study drugs will be administered in the study site under direct observation of study site personnel and recorded in the eCRF. Per standard clinic procedure, study site personnel will perform a mouth check and inspect all dose containers to ensure that the entire dose was administered. Following completion of dosing procedures and return of dosing containers to the pharmacy by team members, pharmacy staff will follow standard clinic procedures for study drug reconciliation. SIGA will provide information to PPD for destruction of returned used and unused TPOXX study drug and study drug bottles.

The date and time of study drug dosing will be captured and recorded on the appropriate page of the eCRF. If a subject is not administered study drug, the reason for the missed dose will be recorded.

Draft Statistical Analysis Plan, Version 2.0 Protocol: SIGA-246-023 Date Issued: 8OCT2022

Treatment compliance, defined as the percentage of capsules consumed, will be summarized by treatment using statistics for continuous variables as well as presented in a listing.

6. Demographics and Baseline Characteristics

6.1 **Demographics**

Demographic information collected at screening will be presented in a data listing. Descriptive statistics will be calculated for the following continuous demographic characteristics:

- Age (years)
- Weight (kg)
- Height (cm)
- Body mass index (BMI) (kg/m²)

Frequency counts and percentages will be tabulated for the categorical variables:

- Sex
- Race
- Ethnicity

The summaries will be presented overall for the safety population.

6.2 **Medical History**

The medical history data will be coded using the Medical Dictionary for Regulatory Activities (MedDRA, version to be delineated in the clinical study report [CSR]) and presented in a data listing.

7. Treatments and Medications

Prior and Concomitant Medications

Medications taken within 30 days prior to the signing of the informed consent form (ICF) up until the first dose of study drug will be classified as prior medications. Medications that start on or after the first dose of study drug will be classified as concomitant.

If a prohibited concomitant medication listed in Section 4.2 of the protocol is taken, it will be documented as a protocol deviation and a joint decision will be made by the investigator and SIGA to continue or discontinue the subject based on the time the medication was administered, its pharmacology and PK, and whether the use of the medication will compromise the safety of the subject or the interpretation of the data.

The investigator is responsible for ensuring that details regarding the medication are adequately recorded in both the subject's source document and the eCRF.

All prior and concomitant medications will be coded according to the World Health Organization Drug Dictionary (version to be delineated in the CSR) and will be summarized by treatment.

Prior and concomitant medications will be presented in a data listing.

Medical or Surgical Treatment Procedures 7.2

Medical or surgical treatment procedures will be presented in a data listing.

7.3 Study Treatment

The study drug administration and drug accountability data as collected on eCRF will be presented in the data listings, including but not limited to the treatment sequence, time point and date, study dose, and reason for adjustment if any.

8. Pharmacokinetics

Individual TPOXX plasma concentration and time data will be presented in a data listing and individual plots based on the safety population, and all summaries and analyses of the PK data of TPOXX will be based on the PK population as defined in Section 4.3.

8.1 Data Handling

The following procedures will be used for plasma concentrations data of TPOXX below the lower limit of quantification (LLOQ) and missing values:

- Concentration values that are below limit of quantification (BLQ) will be reported as provided by the bioanalytical data in the PK data listings.
- For the calculation of concentration summary statistics, BLQ values will be replaced with zero at individual timepoints.
- If the mean concentration value is less than the lower limit of quantitation (LLOQ) value, then the mean concentration value will be set to BLQ in tables with other summary statistics reported as not applicable (NA) except for median, minimum and maximum, where BLQ were reported. The mean concentration plotted as zero in linear scale graphics and missing in semi-logarithmic scale graphics.
- For calculation of PK parameters, BLQ concentration values prior to the first measurable concentration will be set to zero. Post-dose BLQ values after the first quantifiable time point that are followed by measurable concentrations will be set to half the value of LLOQ. Post-dose BLQ value after first quantifiable time point that are not followed by measurable concentrations will be replaced by zero.
- Missing concentration values will not be imputed and will be excluded from the calculations.
- Default significant figures used for reporting in text, tables, and summary statistics of the study report is three significant figures, except for N (number of subjects in the group) and n (number of subjects in the group with reported data), where integer will be presented.

8.2 Pharmacokinetic Concentrations

Blood samples for PK analysis of TPOXX will be collected from all subjects at the following time points: within 60 minutes before dosing (0 hour) and at 0.5, 1, 2, 4, 6, 8, 12, 24, and 48 hours after administration of study drug in each period.

For PK blood samples, the acceptable window for collection from the scheduled collection time point will be as follows: ± 5 minutes for the time points from 0.5 through 8 hours and ± 15 minutes for the time points from 12 through 48 hours.

Individual plasma concentration and time deviation data will be presented in a data listing. Plasma concentration data will be summarized by time point for each treatment using the

following descriptive statistics: number of subjects, arithmetic mean, SD, coefficient of variation (CV), geometric mean, geometric CV, geometric SD, minimum, median, and maximum.

Individual and mean plasma concentration versus scheduled time profiles will be presented in figures on both linear and semilogarithmic scales.

8.3 Plasma Pharmacokinetic Parameters

Plasma concentration-time data will be analyzed by non-compartmental analysis using Phoenix[®] WinNonlin[®] Version 8.3 (Certara USA, Inc., Princeton, NJ). The following plasma PK parameters will be calculated for TPOXX to the extent that data permit using actual sampling times rather than scheduled sampling times:

C_{max}	Maximum drug concentration in plasma
T _{max}	Time of maximum drug concentration in plasma
AUC ₀₋₂₄	Area under the plasma concentration-time curve (AUC) from time 0 to 24 hours, calculated using the linear up log down rule
AUC ₀₋₄₈	AUC from time 0 to 48 hours, calculated using the linear up log down rule
AUC _{0-t}	AUC from time 0 to the last quantifiable concentration, calculated using the linear up log down rule
AUC _{0-inf}	AUC from time 0 extrapolated to infinity, calculated using the linear up log down rule

In addition to the above PK parameters, which will be listed and summarized, the following parameters will also be listed to document the selection of data points used to estimate $t_{1/2}$ using non-compartmental procedures:

λ_{z}	Observed elimination rate constant, where λ_z is the magnitude of the slope of the linear regression of the log concentration versus time profile during the terminal phase
t _{1/2}	Apparent terminal elimination half-life, calculated as: ln (2) / λ_z
Number points	Number of data points used to estimate λ_z ; a minimum of 3 data points must be used, and C_{max} must not be included
λ_z lower	Lower bound used for the estimation of λ_z
λ_z upper	Upper bound used for the estimation of λ_z
Span	Number of elapsed half-lives over which λ_z is estimated, calculated as $(\lambda_z \ upper - \lambda_z \ lower) \ / \ t_{1/2}$
Rsq	r^2 , the coefficient of determination (goodness of fit statistic); λ_z and all associated parameters will only be reported where $r^2 \ge 0.80$.

The individual PK parameters will be presented in data listings and summarized by treatment using the following descriptive statistics: number of subjects, mean, SD, CV, geometric mean, geometric SD, geometric CV, minimum, median, and maximum. T_{max} will be summarized using number of observations, median, minimum, and maximum only.

8.4 Pharmacokinetic Statistical Analysis

A linear mixed model with sequence, treatment, and period as fixed effects and subject within sequence as a random effect will be performed on the natural log-transformed values of AUCs (AUC $_{0-24}$, AUC $_{0-48}$, AUC $_{0-t}$, and AUC $_{0-inf}$) and C $_{max}$ to assess the effect of phosphate binders on the PK of TPOXX. The geometric least square means and corresponding 90% CIs will be computed for AUCs and C $_{max}$ of TPOXX + phosphate binder versus TPOXX alone by taking the anti-log of the least squares means from the linear mixed-effect model on the natural logarithms of the corresponding PK parameters. A 90% CI for the ratio will be constructed as the anti-log of the confidence limits of the mean difference. No adjustment will be made for multiplicity.

It will be concluded that there is no relevant interaction of phosphate binders on TPOXX if the 90% CIs for AUCs and C_{max} ratios (TPOXX + phosphate binder/TPOXX alone) are completely contained within the (80%, 125%) interval.

Non-parametric methods will be used to examine median differences in T_{max} for TPOXX.

The geometric mean ratios and corresponding 90% CIs for AUCs and C_{max} for TPOXX will be presented in forest plots for overall assessment of the DDI.

9. Safety Analysis

All safety summaries and analyses will be based upon the safety population.

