5. STUDY TREATMENTS

5.1 TREATMENTS ADMINISTERED

All subjects will receive the following study treatments as follows:

- Treatment A: A single oral dose of 600 mg (3 × 200 mg capsules) TPOXX.
- Treatment B: A single oral dose of 600 mg (3 × 200 mg capsules) TPOXX coadministered with a single oral dose of 1600 mg (2 × 800 mg tablets) sevelamer carbonate (Renvela® or generic equivalent).
- Treatment C: A single oral dose of 600 mg (3 × 200 mg capsules) TPOXX coadministered with a single oral dose of 500 mg sucroferric oxyhydroxide (Velphoro®) chewable tablet.
- Treatment D: A single oral dose of 600 mg (3 × 200 mg capsules) TPOXX coadministered with a single oral dose of 1334 mg (2 × 667 mg capsules) calcium acetate (PhosLo® or generic equivalent).
- Treatment E: A single oral dose of 600 mg (3 × 200 mg capsules) TPOXX coadministered with a single oral dose of 500 mg lanthanum carbonate (Fosrenol® or generic equivalent) chewable tablet.

There will be a washout period of 7 days between dosing in each treatment period.

[figure not shown]
All subjects will be provided a meal (consisting of approximately 600 calories and 25 g fat). The meal should be completed within 30 minutes. Subjects should be administered study drug as soon as possible following completion of the meal but no more than 30 minutes should elapse between meal completion and study drug administration. All study drug will be administered to subjects by the study site personnel with approximately 240 mL of water.

Study drug and meals must be taken with water only, and no other beverage except water should be ingested within 3 hours before or 3 hours after study drug administration. Water is allowed at all times throughout the study. Subjects must fast for 2 hours after taking study drug as further food consumption may affect drug absorption. Subjects should receive standardized meals that are scheduled at the same time in each period of the study.

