5.3 METHOD OF ASSIGNING SUBJECTS TO TREATMENT GROUPS

Randomization will occur according to the randomization schedule before study drug administration on Day 1 of Period 1 after it has been confirmed that the subject fulfills all eligibility criteria. Subjects will be randomly assigned to receive study drug in 1 of 4 treatment sequences (ABCDE, ACEBD, ADBEC, and AEDCB) in 1:1:1:1 ratio.

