7. STATISTICAL ANALYSIS PLAN

7.1 SAMPLE SIZE CALCULATIONS

The sample size (N = 44 [to allow at least 36 enrolled subjects to complete]) for this study is based on clinical and practical considerations and not on a formal statistical power calculation. The sample size is considered sufficient for the objectives of the study.

Prior estimates of within-subject variability (CV_w) of a single dose of 600 mg TPOXX were obtained from Study SIGA-246-018, which evaluated the single-dose PK of TPOXX in a similar population. The CV_w % for C_{max} , AUC_{0-24} and AUC_{0-inf} ranged from 11.39% to 12.62%, 9.38% to 18.12%, and 15.70% to 18.02%, respectively.

For a sensitivity analysis, a range for CV_w of 10%, 15%, and 20% across point estimates of 0.9, 1.0, and 1.1 will be explored.

For the sensitivity analysis, assuming a range of CV_w , a sample size of 36 evaluable subjects, it is estimated that the precision (ie, half-width of the 90% confidence interval [CI] on the log and ratio scale), and CI with tolerance probability of 80% on the original scale for each point estimate will be:

CVw (%)	Half-Width (log scale)	Half-Width (original scale)	Point Estimate	90% Confidence Interval
10	0.043	0.044	0.9	(0.862, 0.94)
			1.0	(0.958, 1.044)
			1.1	(1.054, 1.148)
15	0.065	0.067	0.9	(0.843, 0.96)
			1.0	(0.937, 1.067)
			1.1	(1.031, 1.174)
20	0.086	0.090	0.9	(0.826, 0.981)
			1.0	(0.918, 1.09)
			1.1	(1.009, 1.199)

Abbreviation: CV_w, within-subject variability.

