4.1. Sample Size

The sample size (N = 44 [to allow at least 36 enrolled subjects to complete]) for this study is based on clinical and practical considerations and not on a formal statistical power calculation. The sample size is considered sufficient for the objectives of the study.

Prior estimates of within-subject variability (CVw) of a single dose of 600 mg TPOXX were obtained from Study SIGA-246-018, which evaluated the single-dose PK of TPOXX in a similar population. The CVw% for Cmax, AUC_{0-24} and AUC_{0-inf} ranged from 11.39% to 12.62%, 9.38% to 18.12%, and 15.70% to 18.02%, respectively.

For a sensitivity analysis, a range for CVw of 10%, 15%, and 20% across point estimates of 0.9, 1.0, and 1.1 will be explored. For the sensitivity analysis, assuming a range of CVw, a sample size of 36 evaluable subjects, it is estimated that the precision (ie, half-width of the 90% confidence interval [CI] on the log and ratio scale), and CI with tolerance probability of 80% on

the original scale for each point estimate will be:

				90%
	Half-Width	Half-Width		Confidence
CVw (%)	(log scale)	(original scale)	Point Estimate	Interval
10	0.043	0.044	0.9	(0.862, 0.94)
			1.0	(0.958, 1.044)
			1.1	(1.054, 1.148)
15	0.065	0.067	0.9	(0.843, 0.96)
			1.0	(0.937, 1.067)
			1.1	(1.031, 1.174)
20	0.086	0.090	0.9	(0.826, 0.981)
			1.0	(0.918, 1.09)
l			1.1	(1.009, 1.199)

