4.3. Analysis Population

The analysis populations are as follows:

- The PK Population will include subjects who receive at least 1 dose of TPOXX and have sufficient concentration data to support accurate estimation of at least 1 PK parameter.
- The Safety Population will include all subjects who receive any amount of study drug.

5. Subject Disposition

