9.5 Electrocardiograms

Single 12-lead ECGs will be obtained after the subject has been in the supine position for at least 10 minutes. A single repeat measurement is permitted at screening for eligibility determination. Electrocardiogram assessments will include comments on whether the tracings are normal or abnormal, rhythm, presence of arrhythmia or conduction defects, morphology, any evidence of myocardial infarction, or ST-segment, T-wave, and U-wave abnormalities.

In addition, measurements of the following intervals will be measured and reported: heart rate; PR, RR, and QT interval; QTcF, QT interval corrected using Fridericia's formula; and QRS duration. All ECGs must be performed by an experienced ECG technician.

Draft Statistical Analysis Plan, Version **2.0**Date Issued: 8OCT2022

SIGA Technologies, Inc. Protocol: SIGA-246-023

Single 12-lead ECG will be performed at the timepoints indicated in the schedule of assessments (schedules of assessments can be found in Section 13).

Actual values at baseline for numeric ECG data will be summarized by visit and treatment for subjects in the safety population.

All ECG data will be presented in a data listing.

10. Interim Analysis

No formal interim analyses will be performed in this study.

11. Changes in the Planned Analysis

Any changes from this statistical analysis plan will be documented in the CSR for this study.

SIGA Technologies, Inc.

Protocol: SIGA-246-023

Draft Statistical Analysis Plan, Version 2.0

Date Issued: 8OCT2022

12. References

- 2. Department of Health and Human Services (DHHS), Food and Drug Administration, Center for Drug Evaluation and Research, Center for Drug Evaluation and Research. Guidance for Industry: Clinical Drug Interaction Studies—Cytochrome P450 Enzyme-and Transporter-Mediated Dug Interactions. January 2020 [cited 24 Jan 2022]. Available from: https://www.fda.gov/media/134581/download.
- 3. Division of AIDS (DAIDS), National Institute of Allergy and Infectious Diseases, National Institutes of Health, US Department of Health and Human Services. Division of AIDS (DAIDS) table for grading the severity of adult and pediatric adverse events. July 2017 [cited 2020 Aug 18]. Available from:
 - https://rsc.niaid.nih.gov/sites/default/files/daidsgradingcorrectedv21.pdf.

13. Schedule of Events

Schedule of Events: Period 1 through Period 3

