- (d) Vital sign measurements included systolic and diastolic blood pressures, heart rate, respiratory rate, and body temperature. Vital signs were measured at screening, and in each period, on Day –1; within 60 minutes prior to dosing; and at 4, 8, 12, 24, and 48 hours following dosing in each period after the subject has been in a seated position for at least 5 minutes.
- (e) Fasting lipid panel included cholesterol (total, high-density lipoprotein, calculated low-density lipoprotein, and triglycerides).
- (f) Clinical laboratory testing included hematology and serum chemistry.
- (g) Clinical laboratory testing at screening included hematology, serum chemistry, and urinalysis.
- (h) For postmenopausal women, a serum follicle-stimulating hormone test was performed at screening.
- (i) Women of childbearing potential only.
- (included alcohol, cotinine, amphetamines (including methamphetamines and ecstasy/methylenedioxymethamphetamine), barbiturates, benzodiazepines, cannabinoids (including tetrahydrocannabinol), cocaine metabolites, and opiates (including heroin, codeine, and oxycodone). A urine drug screen including alcohol and cotinine was collected and sent to the central laboratory at the screening visit. A urine drug screen and alcohol breath test using a breathalyzer was performed and read locally on Day –1.
- (k) Randomization occurred according to the randomization schedule before study drug administration on Day 1 of Period 1 after it has been confirmed that the subject fulfilled all eligibility criteria. Subjects were randomly assigned to receive study drug in 1 of 4 treatment sequences (ABCDE, ACEBD, ADBEC, and AEDCB) in 1:1:1:1 ratio.
- (1) A single 12-lead ECG was obtained after the subject had been in the supine position for at least 10 minutes. On Day 1 of each period, an ECG was recorded 4 hours after study drug administration. The acceptable window for collection from the scheduled collection time point was ±15 minutes.

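### TPOXX alone is given only in Period 1, so the stated mixed model cannot estimate any binder/TPOXX-alone ratio

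*Combined protocol and SAP*

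**What the plan says.** Protocol 5.3 assigns subjects 1:1:1:1 to "1 of 4 treatment sequences (ABCDE, ACEBD, ADBEC, and AEDCB"; the synopsis, protocol 3 and SAP 3 list the same sequences. Treatment A, TPOXX alone, is in Period 1 of each and in no other period.

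SAP 8.4 states the model: "A linear mixed model with sequence, treatment, and period as fixed effects and subject within sequence as a random effect will be performed". It applies to the logs of Cmax and four AUCs. Protocol 7.3.1 and the synopsis give the same model for AUC0-24 and Cmax. All three derive each binder/TPOXX-alone ratio and its 90% CI from that model and conclude no relevant interaction if the CIs lie within 80%-125%.

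None of them mentions that A and Period 1 coincide, and none gives a constraint, an alternative model or an assumption about period effects. On departures from the plan, SAP 11 says only: "Any changes from this statistical analysis plan will be documented in the CSR for this study".

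**The concern.** In a crossover, period can be adjusted for because each treatment appears in several periods. Here the reference treatment appears in one period, and that period contains nothing else. The data cannot separate what A does from what Period 1 does.

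The four binder/A ratios serve the primary objective and are the only basis for the 80%-125% conclusion. Software given this model will either report the contrasts as non-estimable or impose a constraint of its own. If the analyst then picks a repair, both the ratios and their CIs can depend on the pick, which may be made after concentrations have been seen. The alias is visible from the sequence list, so it can be settled beforehand without any data.

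**Working it through.** **Inputs.** Sequences and 1:1:1:1 allocation (protocol 5.3); model and 90% CIs (SAP 8.4); 36 evaluable subjects, CVw 10/15/20% and 80% tolerance probability (protocol 7.1, SAP 4.1). Period is read as a five-level factor. Complete data for 36 subjects means 9 per sequence and 36 × 5 = 180 rows.

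**1. The plan's precision table.** The table gives a "CI with tolerance probability of 80% on the original scale for each point estimate will be" the listed limits. Its half-widths follow from a paired formula:

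half-width = t(0.95, df) × σ × √(k/36) × √(χ²(0.80, df)/df), with σ = √ln(1 + CVw²), k = 2, df = 35.

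At CVw 15%: 1.6896 × 0.1492 × √(2/36) × √(41.78/35) = 0.0649. For 10/15/20% the results are 0.0434/0.0649/0.0862, matching the stated 0.043/0.065/0.086. The variance used, 2σ²/36, holds only if period is omitted or suitably constrained. The table therefore does not describe the stated model.

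**2. Estimability.** The fixed effects need 1 + 3 + 4 + 4 = 12 independent columns (intercept, sequence, treatment, period). The A column equals the Period 1 column, so the rank is 11.

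Add any constant c to the A effect and subtract c from the Period 1 effect: every fitted value is unchanged, but B-A, C-A, D-A and E-A all move by -c. None is estimable. A rank check on the design matrix confirms this and shows that:
- all five treatment least squares means (equal period weights) are non-estimable;
- all six contrasts among B to E are estimable;
- the result is the same with 11 subjects per sequence, with subject columns added, and with simulated dropout.

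The random subject effect does not help, because the alias is among the fixed effects. What is estimable is (binder - A) + (mean of Periods 2-5 - Period 1).

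**3. The constraint decides the answer.** Take noise-free data with true ratios of 1 and exposure 10% lower in Periods 2-5. Setting the Period 1 and Period 5 effects equal gives all four ratios as 0.90. Setting the A and E effects equal gives 1.00. Both fit with residual sum of squares 0.

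**4. Precision under possible repairs (36 completers).**

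| Period term | Rank / columns | Var(binder - A) | Residual df | Half-width, CVw 10/15/20% |
|---|---|---|---|---|
| Five-level, as stated | 11 / 12 | not estimable | – | – |
| Period 1 = 0, Periods 2-5 sum to zero | 11 / 11 | 2.00σ²/36 | 137 | 0.041/0.061/0.081 |
| Omitted | 8 / 8 | 2.00σ²/36 | 140 | 0.041/0.061/0.081 |
| Period 1 tied to one later period | 11 / 11 | 2.75σ²/36 | 137 | 0.048/0.072/0.095 |
| Linear in period number | 9 / 9 | 3.25σ²/36 | 139 | – |

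Tying Period 1 to a single later period raises the standard error by √(2.75/2) = 1.173, or 17%, and gives half-widths above the planned ones. It also moves all four ratios by the difference between that period and the Period 2-5 average.

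**5. What a Period 1 shift could do (illustration only).** Under the sum-to-zero form, a shift in the Period 2-5 average relative to Period 1 multiplies all four ratios. SAP 4.1 reports that prior CVw for Cmax, AUC0-24 and AUC0-inf "ranged from 11.39% to 12.62%, 9.38% to 18.12%, and 15.70% to 18.02%, respectively". At the largest value, 18.12%, the half-width is 0.0736 (k = 2, df 137):
- ratio 0.9: lower limit 0.836, so the CI leaves the interval at 0.80/0.836 = 0.957, a shift of -4.3%;
- ratio 1.1: upper limit 1.184, so 1.25/1.184 = 1.056, or +5.6%;
- ratio 1.0: -13.9% or +16.1%.

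The documents give no evidence of such a shift.

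**The case against.** The strongest reply has four parts.

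- **Period need not be categorical.** The texts say only that period is a fixed effect. With a linear term the contrasts are estimable. This is a fair qualification: the conclusion holds under the ordinary crossover reading. But neither document specifies a linear term, and it would itself be an unstated constraint that extrapolates to Period 1, at 3.25σ²/36.
- **A Period 1 effect is unlikely.** There is a 7-day washout and continuous confinement, and protocol 5.1 adds: "Subjects should receive standardized meals that are scheduled at the same time in each period of the study". This stands as support for assuming no shift. It does not make the contrast estimable, and the assumption is nowhere written down.
- **The no-period model is a weak sensitivity analysis.** This stands. With complete balanced data it gives the same ratios as the sum-to-zero form, so it says nothing about Period 1. The two can differ only with incomplete data, which the PK population admits: "The PK Population will include subjects who receive at least 1 dose of TPOXX" and have data for at least one PK parameter.
- **Editing the protocol is more than a wording change.** Protocol 9.3.6.2.1 sends amendments to the IRB, and protocol 7.3 leaves analysis details to the SAP. This bears on the cost and on where to act first. It leaves the defect untouched.

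**Conclusion.** The concern holds. With period as a five-level factor, the stated model cannot produce any of the primary ratios: 4 of 4 binder/A contrasts per parameter are non-estimable (4 × 2 = 8 in protocol 7.3.1; 4 × 5 = 20 in SAP 8.4), as are 5 of 5 treatment least squares means. This is a property of the sequence list and does not depend on sample size or data. It must be fixed before the ratios are estimated.

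The limits of the point are clear. By-treatment descriptive statistics, safety tables and comparisons among B to E are unaffected. The sample size is not in question: under the sum-to-zero form the planned half-widths are slightly conservative. Nor does the point show that the eventual ratios would be wrong. It shows that the plan does not define how they are obtained.

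**What to change.** In SAP 8.4, and to match in protocol 7.3.1 and the synopsis, replace the free period factor with a stated estimable form. One example is Period 1 coded zero with Period 2-5 deviations summing to zero (three columns), keeping sequence and treatment fixed and subject within sequence random. Report the model without period alongside it, described as a check on imbalance from incomplete data and not on the Period 1 assumption.

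State in the SAP that:
- each binder/A ratio assumes the Period 1 effect equals the average of the Period 2-5 effects;
- this design cannot test that, and any departure multiplies all four ratios by the same factor;
- Tmax comparisons with A share the limitation and are not covered by the model change;
- any tipping shift reported is defined as the Period 2-5 average relative to Period 1.

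The cost is a text change in three places and one explicit, untestable assumption. The SAP is still labelled a draft, so it is the natural place to start; the protocol text goes through the amendment process. No new data or subjects are needed, and with complete data the variance stays at 2σ²/n. No change to randomization is proposed, since SAP 13 note (k) already describes it in the past tense: "Randomization occurred according to the randomization schedule before study drug administration on Day 1 of Period 1".

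### By default SAP 8.4 pools the residual variance over five treatments, while the precision table matches a two-treatment calculation; each binder ratio should have its own prespecified error term

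*Combined protocol and SAP*

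**What the plan says.** SAP 8.4 gives the model for the log-transformed AUCs and Cmax: "A linear mixed model with sequence, treatment, and period as fixed effects and subject within sequence as a random effect will be performed". Protocol 7.3.1 uses the same model for AUC0-24 and Cmax. Neither section names a covariance structure, a residual variance by treatment or a method for the degrees of freedom. No relevant interaction is concluded when the 90% CIs for the binder/TPOXX-alone ratios lie within 80% to 125%.

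On precision, SAP 4.1 (repeated in protocol 7.1) states: "assuming a range of CVw, a sample size of 36 evaluable subjects, it is estimated that the precision" is as tabulated, where precision means the "half-width of the 90% confidence interval [CI] on the log and ratio scale", with a tolerance probability of 80%. The log-scale half-widths are 0.043, 0.065 and 0.086 for CVw 10%, 15% and 20%. Each row uses one CVw, and the analysis assumed is not named.

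The prior CVw estimates "of a single dose of 600 mg TPOXX were" taken from Study SIGA-246-018. For Cmax, AUC0-24 and AUC0-inf they "ranged from 11.39% to 12.62%, 9.38% to 18.12%, and 15.70% to 18.02%, respectively".

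**The concern.** With one random subject effect and no further variance structure, the ordinary reading is a single residual variance shared by TPOXX alone and all four binder treatments. The interval for one binder then takes part of its error from three treatments that are not in the comparison. That is efficient if within-subject variance is the same under all five treatments. If one binder made absorption less consistent, its own interval would be too narrow and those of the other binders too wide. The no-interaction conclusion rests on these intervals alone, so the error term should be chosen on purpose. The precision table appears to have been worked out for a different error term from the one the model implies.

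**Working it through.** **Inputs.** From SAP 4.1: n = 36 evaluable, 90% two-sided CI, 80% tolerance probability, CVw 10%, 15% and 20%, and the prior CVw ranges. From protocol 5.3: sequences ABCDE, ACEBD, ADBEC and AEDCB.

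**1. Reproduce the table.** Log-scale within-subject variance: σ² = ln(1 + CV²). Half-width = t(0.95, df) × √(2σ²/36) × √(χ²(0.80, df)/df).

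At CVw 10%, σ² = 0.00995 and √(2σ²/36) = 0.02351. With 35 df, t = 1.6896 and the tolerance factor is 1.0925, so the half-width is 1.6896 × 0.02351 × 1.0925 = 0.0434.

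| Error term | CVw 10% | 15% | 20% | Rounds to the table? |
|---|---|---|---|---|
| Paired, 35 df | 0.0434 | 0.0649 | 0.0862 | yes |
| 2×2 crossover, 34 df | 0.0435 | 0.0650 | 0.0863 | yes |
| Paired, 35 df, no tolerance factor | 0.0397 | 0.0594 | 0.0789 | no |
| Five treatments pooled, 137 df | 0.0408 | 0.0611 | 0.0811 | no |
| Five treatments pooled, 140 df | 0.0408 | 0.0610 | 0.0810 | no |

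The pooled df are those left from 36 × 5 = 180 observations after fitting subject and treatment, with period (137) or without it (140). Only 34 to 38 df round to the stated values. The table is wider than the pooled model by 0.0434/0.0408 = 1.06, that is, about 6%.

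**2. Does the stated model yield the ratio?** TPOXX alone occupies Period 1 in every sequence, so the indicator for treatment A equals the indicator for Period 1. The fixed-effect matrix has 12 columns and rank 11, and none of the four binder-versus-A contrasts is estimable (B versus C is). Restricting the data to A and one binder does not help: the binder indicator is then the sum of the Period 2 to 5 indicators. The results below therefore assume no period term.

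**3. Effect of pooling if variances differed.** Assumption: one binder at CVw 18.12%, TPOXX alone and the other three binders at 9.38% (the ends of the AUC0-24 range), n = 36.

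- σ² = 0.03231 and 0.00876, a ratio of 3.7.
- Variance used by the pooled model: (4 × 0.00876 + 0.03231)/5 = 0.01347.
- Variance that applies to this contrast: (0.00876 + 0.03231)/2 = 0.02053.
- Ratio of standard errors: √(0.01347/0.02053) = 0.81.
- 90% half-widths without the tolerance factor: pooled 1.6558 × √(2 × 0.01347/36) = 0.0453; paired 1.6896 × √(2 × 0.02053/36) = 0.0571.
- Normal approximation: 1.645 × 0.81 = 1.332, so coverage is 81.7% and the one-sided error at a bound is 9.1%.
- Simulation (100,000 trials): coverage 81.9% pooled and 90.0% paired; false no-interaction at a true ratio of 0.80, 9.0% pooled and 4.9% paired.
- The other three binders: CIs √(0.01347/0.00876) = 1.24 times as wide as they should be, coverage about 96%.

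**4. Same calculation at the other two ranges.** Cmax (11.39% and 12.62%): coverage 88.9%, error at the bound 5.5%. AUC0-inf (15.70% and 18.02%): coverage 88.5%, error 5.7%.

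**5. Price of the paired error if variances are equal.** At CVw 15% the average half-width is 0.0590 paired and 0.0581 pooled, about 1.5% wider.

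**The case against.** A common residual variance is a conventional choice for a crossover mixed model, and nothing in the documents shows it to be wrong here. That objection largely stands. Three stronger readings are tempting, and the documents do not support them.

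- *The prior data show unequal variances.* A reader might infer this from the AUC0-24 range of 9.38% to 18.12%. Those figures are estimates for TPOXX 600 mg from an earlier study. No binder is mentioned, and the documents do not say what the range runs over. The near two-fold spread (18.12/9.38 = 1.93) also holds for AUC0-24 only; it is 1.11 for Cmax and 1.15 for AUC0-inf.
- *The table mismatch is evidence of unequal variance, or of overstated precision.* The table also uses a single CVw for both treatments in each row. It differs from the pooled model only in degrees of freedom, in the cautious direction, and SAP 4.1 says that N does not rest on a power calculation.
- *The trial has a 9% risk of a wrong conclusion.* The figure is for one parameter, at a true ratio exactly on the bound. SAP 8.4 requires four AUCs and Cmax to pass together (protocol 7.3.1: AUC0-24 and Cmax), so for a given binder it is an upper limit. In the same scenario at a true ratio of 0.78 the rates are about 1.8% pooled and 0.8% paired; at 0.75 both are below 0.1%.

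What the objection does not remove is that the error term is unspecified, that the default differs from the one behind the table, and that the robust alternative costs very little.

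**Conclusion.** The point holds as a matter of specification and robustness. By default SAP 8.4 pools the residual variance over five treatments, while the published half-widths are those of a two-treatment calculation and about 6% conservative for the pooled model. Any harm from pooling depends on unequal variances, which the documents do not show. Under the assumption of one binder at 18.12% and the rest at 9.38%, coverage falls to about 82% and the per-parameter error at a bound rises from 5% to about 9%. At the Cmax and AUC0-inf ranges coverage stays near 89%. Half-widths of 0.045 or 0.057 are small against ln(1.25) = 0.223, so the conclusion changes only for ratios close to 80% or 125%. All of these figures assume no period term, because with period fixed the stated model gives no binder-versus-alone interval at all.

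**What to change.** In SAP 8.4 and protocol 7.3.1:

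1. Resolve the aliasing of TPOXX alone with Period 1 first. Neither the five-treatment nor the two-treatment fit can estimate the ratio with period as a fixed effect.
2. Then estimate each binder/TPOXX-alone ratio from within-subject log differences: a paired analysis with no period term, 35 df at n = 36, which matches the table. Alternatively, keep one model without the aliased period term, with a separate residual variance per treatment and Kenward-Roger df.
3. State that either analysis assumes no period effect between Period 1 and later periods. The design cannot test this.
4. If the pooled error is kept, restate the half-widths in SAP 4.1 and protocol 7.1 as about 0.041, 0.061 and 0.081, and report the paired analysis as a sensitivity analysis.

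The cost is a change of wording and a few lines of code. Intervals become about 1.5% wider if variances are equal, which the published table already allows for. In the paired analysis, a subject without a value for both treatments drops out of that comparison.
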